### **5.2.1.2 Dose Modification**

Adverse events (both non-serious and serious) associated with pembrolizumab exposure may represent an immunologic etiology. These adverse events may occur shortly after the first dose or several months after the last dose of treatment. Pembrolizumab must be withheld for drug-related toxicities and severe or life-threatening AEs as per [Table 3](#) below. See Section 5.6 and the Events of Clinical Interest Guidance Document for supportive care guidelines, including use of corticosteroids.

Table 3 Dose Modification and Toxicity Management Guidelines for Immune-related AEs Associated with Pembrolizumab

General instructions:				

 
1. Corticosteroid taper should be initiated upon AE improving to Grade 1 or less and continue to taper over at least 4 weeks.
 
2. For situations where pembrolizumab has been withheld, pembrolizumab can be resumed after AE has been reduced to Grade 1 or 0 and corticosteroid has been tapered. Pembrolizumab should be permanently discontinued if AE does not resolve within 12 weeks of last dose or corticosteroids cannot be reduced to <math>\leq 10</math> mg prednisone or equivalent per day within 12 weeks.
 
3. For severe and life-threatening irAEs, IV corticosteroid should be initiated first followed by oral steroid. Other immunosuppressive treatment should be initiated if irAEs cannot be controlled by corticosteroids.
 
				
Immune-related AEs	Toxicity grade or conditions (CTCAEv4.0)	Action taken to pembrolizumab	irAE management with corticosteroid and/or other therapies	Monitor and follow-up
Pneumonitis	Grade 2	Withhold	
 
• Administer corticosteroids (initial dose of 1-2 mg/kg prednisone or equivalent) followed by taper
 
	
 
• Monitor subjects for signs and symptoms of pneumonitis
 
• Evaluate subjects with suspected pneumonitis with radiographic imaging and initiate corticosteroid treatment
 
• Add prophylactic antibiotics for opportunistic infections
 

	Grade 3 or 4, or recurrent Grade 2	Permanently discontinue		

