Hyperthyroidism	Grade 2	Continue	
 
Treat with non-selective beta-blockers (eg, propranolol) or thionamides as appropriate
 
	
 
Monitor for signs and symptoms of thyroid disorders.
 

	Grade 3 or 4	Withhold or permanently discontinue 		
Hypothyroidism	Grade 2-4	Continue	
 
Initiate thyroid replacement hormones (eg, levothyroxine or liothyronine) per standard of care
 
	
 
Monitor for signs and symptoms of thyroid disorders.
 

Nephritis and Renal dysfunction	Grade 2	Withhold	
 
Administer corticosteroids (prednisone 1-2 mg/kg or equivalent) followed by taper.
 
	
 
Monitor changes of renal function
 

	Grade 3 or 4	Permanently discontinue		

Immune-related AEs	Toxicity grade or conditions (CTCAEv4.0)	Action taken to pembrolizumab	irAE management with corticosteroid and/or other therapies	Monitor and follow-up
Myocarditis	Grade 1 or 2	Withhold	
 
Based on severity of AE administer corticosteroids
 
	
 
Ensure adequate evaluation to confirm etiology and/or exclude other causes
 

	Grade 3 or 4	Permanently discontinue		
All other immune-related AEs	Intolerable/persistent Grade 2	Withhold	
 
Based on type and severity of AE administer corticosteroids
 
	
 
Ensure adequate evaluation to confirm etiology and/or exclude other causes
 

	Grade 3	Withhold or discontinue based on the type of event. Events that require discontinuation include and not limited to: Guillain-Barre Syndrome, encephalitis		
	Grade 4 or recurrent Grade 3	Permanently discontinue		

1. Withhold or permanently discontinue pembrolizumab is at the discretion of the investigator or treating physician.
 
NOTE:            For subjects with Grade 3 or 4 immune-related endocrinopathy where withhold of pembrolizumab is required, pembrolizumab may be resumed when AE resolves to <math>\leq</math> Grade 2 and is controlled with hormonal replacement therapy or achieved metabolic control (in case of T1DM).
				

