In case toxicity does not resolve to Grade 0-1 within 12 weeks after last infusion, trial treatment should be discontinued after consultation with the Sponsor. With investigator and Sponsor agreement, subjects with a laboratory adverse event still at Grade 2 after 12 weeks may continue treatment in the trial only if asymptomatic and controlled. For information on the management of adverse events, see Section 5.6.1.

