### **7.1.3.1 Laboratory Safety Evaluations (Hematology, Chemistry and Urinalysis)**

Laboratory tests for hematology, chemistry, urinalysis, and others are specified in [Table 7](#).

Table 7 Laboratory Tests

Hematology‡	Chemistry	Urinalysis	Other
Hematocrit	Albumin	Blood	Serum $\beta$ -human chorionic gonadotropin ( $\beta$ -hCG)†
Hemoglobin	Alkaline phosphatase	Glucose	PT (INR)
Platelet count	Alanine aminotransferase (ALT)	Protein	aPTT
WBC (total and differential)	Aspartate aminotransferase (AST)	Specific gravity	Total triiodothyronine (T3)¶
Red Blood Cell Count	Lactate dehydrogenase (LDH)	Microscopic exam, if abnormal results are noted†	Free thyroxine (T4)
Absolute Neutrophil Count	Carbon Dioxide§ (CO 2 or bicarbonate)	Urine pregnancy test*	Thyroid stimulating hormone (TSH)
Absolute Lymphocyte Count	Creatinine††		Anti-MK-3475 Antibodies
	Uric Acid		PK
	Calcium		Blood for FBR
	Chloride		Blood for correlative studies
	Glucose		
	Phosphorus		
	Potassium		
	Sodium		
	Magnesium		
	Total Bilirubin		
	Direct Bilirubin, if total bilirubin is elevated above the upper limit of normal		
	Total protein		
	Blood Urea Nitrogen		

† Perform on women of childbearing potential only. If urine pregnancy results cannot be confirmed as negative, a serum pregnancy test will be required.  
‡ Either differential or absolute value is acceptable  
§ If considered standard of care in your region  
¶ Institutional standards are acceptable  
¶ Free T3 may be performed in place of Total T3 per local standards  
†† GFR (measured or calculated) or CrCl can be used in place of creatinine

Laboratory tests for screening or entry into the Second Course Phase should be performed within 10 days prior to the first dose of treatment. After Cycle 1, pre-dose laboratory procedures can be conducted up to 72 hours prior to dosing. Results must be reviewed by the investigator or qualified designee and found to be acceptable prior to each dose of trial treatment.

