### 3. Additional adverse events:

A separate guidance document has been provided entitled “Event of Clinical Interest Guidance Document” (previously entitled “Event of Clinical Interest and Immune-Related Adverse Event Guidance Document”). This document can be found in the administrative binder and provides guidance regarding identification, evaluation and management of ECIs and irAEs.

Subjects should be assessed for possible ECIs prior to each dose. Lab results should be evaluated and subjects should be asked for signs and symptoms suggestive of an immune-related event. Subjects who develop an ECI thought to be immune-related should have additional testing to rule out other etiologic causes. If lab results or symptoms indicate a possible immune-related ECI, then additional testing should be performed to rule out other etiologic causes. If no other cause is found, then it is assumed to be immune-related.

Events of clinical interest that occur to any subject from the date of first dose through 90 days following cessation of treatment, or 30 days after the end of treatment if the subject initiates new anticancer therapy, whichever is earlier, whether or not related to the Sponsor's product, must be reported within 24 hours to the Sponsor either by electronic media or paper. Sponsor Contact information can be found in the administrative binder.

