	Dechallenge	Was the Sponsor's product discontinued or dose/exposure/frequency reduced? If yes, did the AE resolve or improve? If yes, this is a positive dechallenge. If no, this is a negative dechallenge. (Note: This criterion is not applicable if: (1) the AE resulted in death or permanent disability; (2) the AE resolved/improved despite continuation of the Sponsor's product; or (3) the trial is a single-dose drug trial; or (4) Sponsor's product(s) is/are only used one time.)
	Rechallenge	Was the subject re-exposed to the Sponsor's product in this study? If yes, did the AE recur or worsen? If yes, this is a positive rechallenge. If no, this is a negative rechallenge. (Note: This criterion is not applicable if: (1) the initial AE resulted in death or permanent disability, or (2) the trial is a single-dose drug trial); or (3) Sponsor's product(s) is/are used only one time). NOTE: IF A RECHALLENGE IS PLANNED FOR AN ADVERSE EVENT WHICH WAS SERIOUS AND WHICH MAY HAVE BEEN CAUSED BY THE SPONSOR'S PRODUCT, OR IF REEXPOSURE TO THE SPONSOR'S PRODUCT POSES ADDITIONAL POTENTIAL SIGNIFICANT RISK TO THE SUBJECT, THEN THE RECHALLENGE MUST BE APPROVED IN ADVANCE BY THE U.S. CLINICAL MONITOR AS PER DOSE MODIFICATION GUIDELINES IN THE PROTOCOL.
	Consistency with Trial Treatment Profile	Is the clinical/pathological presentation of the AE consistent with previous knowledge regarding the Sponsor's product or drug class pharmacology or toxicology?
The assessment of relationship will be reported on the case report forms /worksheets by an investigator who is a qualified physician according to his/her best clinical judgment, including consideration of the above elements.		
Record one of the following	Use the following scale of criteria as guidance (not all criteria must be present to be indicative of a Sponsor's product relationship).	
Yes, there is a reasonable possibility of Sponsor's product relationship.	There is evidence of exposure to the Sponsor's product. The temporal sequence of the AE onset relative to the administration of the Sponsor's product is reasonable. The AE is more likely explained by the Sponsor's product than by another cause.	

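### Table 3 withholds pembrolizumab for Grade 1 or 2 myocarditis, the general restart rule accepts Grade 1, and the protocol does not say which governs

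*Combined protocol and SAP*

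**What the plan says.** Section 5.2.1.2 makes withholding mandatory as set out in Table 3. The myocarditis row withholds at Grade 1 or 2 and stops permanently at Grade 3 or 4. Its management column leaves corticosteroid use to severity. Its monitoring column asks for a work-up of the cause. Neither gives a restart grade.

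Restart is covered by the general instructions at the head of the table:

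- Instruction 1: "Corticosteroid taper should be initiated upon AE improving to Grade 1 or less and continue to taper over at least 4 weeks".
- Instruction 2, for any situation where drug was withheld: "pembrolizumab can be resumed after AE has been reduced to Grade 1 or 0 and corticosteroid has been tapered". It continues: "Pembrolizumab should be permanently discontinued if AE does not resolve within 12 weeks of last dose".

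The paragraph after the table expresses the 12-week stop in grades: "In case toxicity does not resolve to Grade 0-1 within 12 weeks after last infusion, trial treatment should be discontinued".

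The only different restart grade is in the NOTE under the table, for Grade 3 or 4 endocrinopathy: "pembrolizumab may be resumed when AE resolves to" Grade 2 or below, provided that the condition is also controlled. Section 5.6.1 (Supportive Care Guidelines) has no myocarditis entry.

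**The concern.** A restart threshold normally sits below the grade that triggered the hold. For myocarditis it does not: Grade 1 is both a grade at which to withhold and a grade at which the general rule lets dosing resume. Two sites could handle the same patient differently and each believe it was following the protocol. At stake is re-exposure of a subject with unresolved myocarditis, the event that Table 3 treats most strictly at low grade. The Summary of Changes says that this amendment expanded the guidance and added myocarditis so as to give comprehensive management instructions. A hold without a clear restart grade falls short of that aim.

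**Working it through.** No plan figure needs reproducing. The check is a comparison of texts.

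**Step 1. The two sets of grades for myocarditis.**

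- Withhold (myocarditis row): {1, 2}
- Resume (instruction 2): {0, 1}
- In both: {1}

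**Step 2. Is this general to the table?** The lowest grade at which each row can lead to withholding is:

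| Table 3 row | Lowest withhold grade | Overlaps {0, 1}? |
|---|---|---|
| Pneumonitis | 2 | No |
| Diarrhea/colitis | 2 | No |
| AST/ALT or bilirubin | 2 | No |
| T1DM/hyperglycemia | 3 (new-onset T1DM is ungraded) | No |
| Hypophysitis | 2 | No |
| Hyperthyroidism | 3 | No |
| Hypothyroidism | none (drug continues) | n/a |
| Nephritis/renal dysfunction | 2 | No |
| Myocarditis | 1 | **Yes** |
| All other immune-related AEs | 2 | No |

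Of the ten rows, nine can lead to withholding. One of those nine overlaps instruction 2.

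**Step 3. The path to redosing.** A Grade 2 case is withheld and improves to Grade 1. If steroids were given, instruction 1 starts the taper at that point and runs it for at least 4 weeks. Taking tapered to mean that the taper is complete, instruction 2 is met from about 4 weeks after Grade 1 is reached, with the event still at Grade 1. If no steroid was given, which the row allows, no minimum wait applies.

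**Step 4. Does other text settle it?**

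- *12-week stop.* Instruction 2 speaks only of the event resolving. The following paragraph speaks of resolving to Grade 0-1 and can be read as the definition. It does not require Grade 0.
- *Endocrinopathy NOTE.* It does not cover myocarditis.
- *Rechallenge, Table 8 in Section 7.2.4.* For a serious event possibly caused by the drug, or where re-exposure adds potential significant risk, "THEN THE RECHALLENGE MUST BE APPROVED IN ADVANCE BY THE U.S. CLINICAL MONITOR AS PER DOSE MODIFICATION GUIDELINES IN THE PROTOCOL". This is a real control, but it sends the reader back to the text in question.
- *Checks before each dose.* Section 7.2.3.2: "Subjects should be assessed for possible ECIs prior to each dose". Section 7.1.3.1, on laboratory tests: "Results must be reviewed by the investigator or qualified designee and found to be acceptable prior to each dose of trial treatment". Neither names a grade at which dosing may restart.

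No text reviewed gives a restart grade specific to myocarditis.

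**The case against.** **The specific row overrides the general permission.** Withholding is mandatory under the opening of Section 5.2.1.2, the row names Grade 1, and instruction 2 only says that drug can be resumed. Reading the mandatory, specific text over the permissive, general one is ordinary, and it is the safe result. This stands as a possible reading, and it is why confidence is moderate. It does not remove the point. Instruction 2 is part of the same table, its scope excludes no row, and no precedence is stated. The override reading also leads to a Grade 0 restart, which the fix would simply write down.

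**Entry and restart thresholds may differ by design.** The row says what to do when the event appears; instruction 2 deals with a treated, improving event. Hypophysitis is withheld at Grade 2, yet after a Grade 3 or 4 episode the NOTE lets dosing resume at Grade 2 or below. So a lower bar for restart would be coherent. But the NOTE states its exception openly and adds a control condition. Myocarditis has no such statement. If restart at Grade 1 is intended, the row should say so.

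**Existing controls suffice.** Redosing is optional, and the significant-risk limb of the rechallenge rule may well reach non-serious myocarditis. These controls may catch some cases. They leave the person deciding without a grade to apply.

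**A stronger reading to avoid.** A reader might infer that milder disease meets the stricter rule, because an event starting at Grade 1 can only be reduced to Grade 0. The same words can equally mean that such an event already sits at an accepted grade. The documents do not decide between these, so the point does not rely on it.

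**Conclusion.** The inconsistency is real but minor. At Grade 1 myocarditis, Table 3 supports both withholding and optional redosing, and does not say which rule prevails.

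Two further inferences go beyond the documents. A reader might conclude that the protocol plainly authorises redosing at Grade 1; it does so on one reading only, and nowhere automatically. A reader might also want to attach a probability. That would need the number of subjects treated or retreated after this amendment, the myocarditis rate, and the share of Grade 2 cases that settle at Grade 1. The documents give none of these. The planned total of 114 + 110 = 224 is not the right base, because the row came in with this amendment. An any-grade rate would also overstate the problem, because Grade 3 or 4 cases stop permanently.

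The number affected should be very small: one event type, one grade path, and a trial already due to roll over into an extension study. There is no effect on ORR, power or sample size. Confidence is moderate because the override reading is available.

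**What to change.** Add one line to the myocarditis row: *Exception to general instruction 2: resume only when myocarditis has resolved to Grade 0 and any corticosteroid has been tapered.*

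The cost is one line by amendment. The downside is that a few subjects with persistent Grade 1 findings wait longer or do not restart.

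The line should not by itself force permanent discontinuation at 12 weeks for persistent Grade 1. A reader might expect that to follow, but the documents do not support it; it is a clinical choice for the sponsor. Section 7.1.1.9 already requires a documented decision between investigator and sponsor when toxicity interrupts dosing for more than 12 weeks, and that can handle such cases. If the sponsor instead intends Grade 1 restarts, the row should say so expressly.

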### **5.2.2 Timing of Dose Administration**

Trial treatment should be administered on Day 1 of each cycle after all procedures/assessments have been completed as detailed on the Trial Flow Chart (Section 6.0). Trial treatment may be administered up to 3 days before or after the scheduled Day 1 of each cycle due to administrative reasons.

All trial treatments will be administered on an outpatient basis.

Dosing interruptions are permitted in the case of medical / surgical events or logistical reasons not related to study therapy (e.g., elective surgery, unrelated medical events, subject vacation, and/or holidays). Subjects should be placed back on study therapy within 3 weeks of the scheduled interruption, unless otherwise discussed with the Sponsor. The reason for interruption should be documented in the patient's study record

MK-3475 will be administered as a 30 minute IV infusion every 2 or 3 weeks depending on the Cohort the subjects have been enrolled into. Sites should make every effort to target infusion timing to be as close to 30 minutes as possible. However, given the variability of infusion pumps from site to site, a window of -5 minutes and +10 minutes is permitted (i.e., infusion time is 30 minutes: -5 min/+10 min).

The Pharmacy Manual contains specific instructions for MK-3475 dose calculation, reconstitution, preparation of the infusion fluid, and administration.

### **Treatment after initial evidence of radiologic disease progression**

Immunotherapeutic agents such as MK-3475 may produce antitumor effects by potentiating endogenous cancer-specific immune responses. The response patterns seen with such an approach may extend beyond the typical time course of responses seen with cytotoxic agents, and can manifest as a clinical response after an initial increase in tumor burden or even the appearance of new lesions.

If radiologic imaging shows PD, tumor assessment should be repeated  $\geq 4$  weeks later in order to confirm PD with the option of continuing treatment per below while awaiting radiologic confirmation of progression. If repeat imaging shows a reduction in the tumor burden compared to the initial scan demonstrating PD, treatment may be continued as per treatment calendar. If repeat imaging confirms progressive disease, subjects will be discontinued from study therapy (exception noted in Section 7.1.2.5.1). In determining whether or not the tumor burden has increased or decreased, Investigators should consider all target lesions as well as non-target lesions (please refer to the Site Imaging Manual).

When feasible, subjects should not be discontinued until progression is confirmed; however, the decision to continue study treatment after the 1st evidence of disease progression is at the Investigator’s discretion based on the clinical status of the subject as described in [Table 4](#) below. Subjects may receive study treatment while waiting for confirmation of PD if they are clinically stable as defined by the following criteria:

- Absence of signs and symptoms (including worsening of laboratory values) indicating disease progression
- No decline in ECOG performance status
- Absence of rapid progression of disease
- Absence of progressive tumor at critical anatomical sites (e.g., cord compression) requiring urgent alternative medical intervention

Table 4 Imaging and Treatment After 1st Radiologic Evidence of PD

	Clinically Stable		Clinically Unstable	
	Imaging	Treatment	Imaging	Treatment
1 st radiologic evidence of PD	Repeat imaging at $\geq 4$ weeks to confirm PD	May continue study treatment at the Investigator’s discretion while awaiting confirmatory scan	Repeat imaging at $\geq 4$ weeks to confirm PD if possible	Discontinue treatment
Repeat scan confirms PD	No additional imaging required	Discontinue treatment (exception noted in Section 7.1.2.5.1)	No additional imaging required	N/A
Repeat scan shows SD, PR or CR	Continue regularly scheduled imaging assessments every 8 weeks	Continue study treatment at the Investigator’s discretion	Continue regularly scheduled imaging assessments every 8 weeks	May restart study treatment if condition has improved and/or clinically stable per Investigator’s discretion

### 5.2.3 Trial Blinding/Masking

This is an open-label trial; therefore, the Sponsor, investigator and subject will know the treatment administered.

PD-L1 IHC biomarker testing is used to determine study eligibility for Cohorts A, B, C, and D and therefore the subject, investigator and SPONSOR will know the PD-L1 IHC result. Access to PD-L1 subject-level biomarker results for subjects enrolled in Cohort B2 will be

limited to an unblinded SPONSOR statistician, and unblinded SPONSOR statistical programmer who will be responsible for data review to ensure validity of results and summary reporting of clinical response by biomarker status, but who will have no other responsibilities associated with the study.

### **5.3 Randomization or Treatment Allocation**

Subjects participating in this trial will be allocated to trial treatment by non-random assignment.

### **5.4 Stratification**

No stratification based on age, sex or other characteristics will be used in this trial.

### **5.5 Concomitant Medications/Vaccinations (allowed & prohibited)**

Medications or vaccinations specifically prohibited in the exclusion criteria are not allowed during the ongoing trial. Listed below are some specific restrictions for concomitant therapy or vaccination during the course of the trial. If there is a clinical indication for one of these or other medications or vaccinations specifically prohibited during the trial, discontinuation from trial therapy or vaccination may be required. The investigator should discuss any questions regarding this with the local Clinical Monitor. The final decision on any supportive therapy or vaccination rests with the investigator and/or the subject's primary physician. However, the decision to continue the subject on trial therapy or vaccination schedule requires the mutual agreement of the investigator, the Sponsor and the subject.

